#### 7.1.1 Vomiting

Vomiting in study and use of anti-emetic agents in participants will be recorded and incidence will be compared in intervention and placebo groups. In the event of emesis, enteral study infusion will be temporarily discontinued and will be restarted per ICU management guidelines for enteral infusions. Gastric residuals will not be monitored in this study.

#### 7.1.2 Diabetic ketoacidosis and hyperglycemia hyperosmolar syndrome (HHS)

The development of either diabetic ketoacidosis or hyperglycemic hyperosmolar syndrome during the intervention period of this study will prompt cessation of enteral infusion to allow for the strict control of caloric delivery required in the treatment of these syndromes.

#### 7.1.3 Ischemic bowel

Ischemic bowel is a rare and potentially serious complication associated with enteral feeding occurring in less than 1% of patients. Ischemic bowel presents with intolerance to enteral feedings manifested by emesis, abdominal pain, or bloating and is characterized by ischemia or necrosis of the intestinal tissue thought to be related to diversion of blood flow to intestinal blood vessels in response to

enteral nutrients during periods of hypotension and shock. By utilizing only dextrose this risk is expected to be minimal.

## **7.2 Reportable severe adverse events**

Critically ill septic patients represent a population in whom life-threatening multi-organ dysfunction and a high rate of untoward medical events are commonly seen routinely during their clinical course as part of their presenting medical condition. In an effort to document only clinically-relevant untoward medical events that have a greater likelihood of being study related, study endpoints (including level of glycemic control, incidence of emesis, incidence of hypotension) and certain pre-specified expected events for critically ill septic patients (see Appendix 11.3) will not be reported as serious adverse events if they occur during the 24-hour intervention period. Reportable serious adverse events (defined as fatal or immediately life-threatening or those that are permanently disabling) that are unexpected and are suspected to be related to study interventions will be disclosed within 24 hours to the IRB.

## **7.3 Monitoring for adverse events**

Participants will be assessed for adverse events by both the study investigators and by the treating ICU team during 24 hours of study intervention. Record of adverse events in the usual care and intervention arms will be made available to the DSMB.

## **7.4 Indications for study discontinuation**

The following indications will be criteria for study discontinuation:

- Request by participant.
- Serious adverse event related to intervention.
- Medical need to hold further enteral infusions including impending intra-abdominal surgery.
- Clinical evaluation by either the investigator or ICU physician that continuation of the intervention would be unsafe including blood glucose greater than 500 mg/dL, severe ileus, or development of severe abdominal pain or emesis related to study intervention.
- Discretion of the investigator.
- Decision by data safety and monitoring board to discontinue enrollment.

## **7.5 Protocol adherence**

Participants in both the placebo and intervention group will be assessed to determine the (1) the number of interruptions in enteral study infusion and (2) total amount of time that enteral study infusion was successfully administered during the 24 hour intervention period.

## **7.6 Clinical nutrition management**

The clinical ICU team will be encouraged by study investigators to avoid the use of dextrose-containing intravenous infusions and enteral tube feed formulations during the 24 hour intervention period. Study infusions will not be given concomitantly with enteral tube feeds. If enteral tube feeds are started during the intervention period, the study infusion will be stopped and the total time the study infusion was delivered will be recorded. Research specimens will still be collected for these participants. After the 24 hour intervention period, further nutrition support (if any) will be at the discretion of the clinical ICU team.

## **7.7 Data Safety and Monitoring Plan (DSMP)**

The data safety and monitoring plan for this research study will be conducted by a local Data Safety and Monitoring Board (DSMB) that will be created to review this study. The individuals to be chosen for the DSMB will be free from financial and academic conflicts, will not include study investigators, and will have the expertise required to understand and identify any issues that would arise with the conduct of a clinical trial in critically ill patients.

The DSMB will meet every six months to review: (1) trial performance with a focus on recruitment, (2) protocol adherence, (3) completeness of data management, and (4) trial safety.

Furthermore, monthly meetings for the monitoring of individual case review will be conducted by the Principal Investigators and research team with review of the following items: recruitment, enrollment, retention, all adverse events, unanticipated problems, withdrawals and any breaches of confidentiality. A regular review of accrued data will be done to ensure data integrity and validity and to ensure that there is no change in the risk to benefit ratio of the study. Any serious or unexpected adverse events, unexpected problems that involve risk to the participants or others, or breaches of confidentiality will be reported to the Institute Review Board (IRB) in compliance with IRB Policies and Procedures. Reporting to the NIH will be the responsibility of the Principal Investigator and the research team.

All Serious Adverse Event reporting to the IRB will occur within 24 hours of notification to the Principal Investigator and or research team for appropriate action and file reporting in accordance with the IRB's stated policy for reporting adverse events. If an unexpected adverse event occurs, the investigators will re-assess the risk/benefit ratio of the study and submit any modifications deemed necessary to the IRB for approval. At the time of the IRB renewal the PI will submit in writing the information about the frequency of the monitoring, the dates that the monthly meetings took place, any external factors or relevant information that might have an impact on the safety or ethics of the study, and final recommendations related to the continuation, changing, or termination of the study.

### **7.7.1 Required education in the protection of human research participants**

Most participants are expected to have cognitive impairment at some time during the study given that study population was specifically selected to be high risk for delirium and long-term cognitive impairment due to sepsis. This vulnerable population cannot be substituted since these forms of cognitive impairment are the focus of our investigation.

All participants who are enrolled when cognitively impaired will be given the opportunity to consent to further participation (or to withdraw) once they regain decision making capacity. Both participants and their authorized representatives can choose to withdraw the participant from the study at any time.

All principal and co-investigators listed on Institutional Review Board-approved protocols at University of Pittsburgh are required to participate in a course entitled "The Education and Certification Program in Research & Practice Fundamentals (RPF)". This web-based tutorial is a requirement of the IRB for protocol submission.

The University of Pittsburgh requires registration of all principal and co-investigators on the Pitt CITI Access Portal. The Collaborative Institutional Training Initiative (CITI) is an organization whose goal is to develop and distribute high quality, peer reviewed educational resources for the research investigators. CITI training programs have become the de facto standard to meet Responsible Conduct of Research (RCR) and Human Subjects Research training requirements at most institutions in the United States. Certifications in Responsible Conduct of Research and Human Subjects Research (either biomedical or social/behavioral) are required for individuals conducting research projects involving human subjects. Further information on training required at the University of Pittsburgh may be found at the following website: <http://www.rcco.pitt.edu/ResearchTrainingRequirements.htm>.

## 8.0 DATA MANAGEMENT AND TRACKING

Data collected during this randomized clinical trial will be stored on an electronic database on the password-protected UPMC network. Any printed documents containing relevant data from the clinical trial will be stored in a locked cabinet in the office of [name] in UPMC Montefiore Hospital. [name] will be responsible for monitoring the security and confidentiality of the database and associated protected health information including participant name, date of birth, and medical record number on a monthly basis. Quality control for the database will be performed with range checks and inspection of any outlier values by [name] or [name].

The electronic medical record of participants will be accessed to obtain patient demographics, hemodynamic parameters, and laboratory and imaging results relevant to determining the severity of illness. The only individuals who will access identifiable medical record information are those who already have (or will have been given) access to the identifiable medical records, granted by the privacy office, by means of their job responsibilities. [name] and [name] have legitimate access to these medical records as part of their clinical responsibilities.

## 9.0 DATA COLLECTION AND STATISTICAL CONSIDERATIONS

### 9.1 Sample size and power calculation

Prior published estimates of cytokine levels in septic patients at 24 hours, suggest that recruitment of 7 patients in each group will provide 90% power to detect a 15% difference in IL-6 with an alpha error of 0.05 (Table 9.1). However, we will need to consider the risk of unbalanced baseline characteristics in our sample and allow for dropouts as well. Therefore, 36 patients will be enrolled in each group, which will provide greater than 90% power to detect 15% difference in IL-6. In our septic mouse model, early initiation of enteral dextrose reduced levels of IL-6 by a much larger amount (~40%) than we are currently powering our clinical trial.

Difference	Power	IL-6
15%	80%	6
15%	90%	7
20%	80%	4
20%	90%	5

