### **5.2.3 Baseline evaluation and randomization:**

If pre-entry evaluation is acceptable, the participant will be enrolled in the study and undergo baseline testing included in Section 5.4.3. At that point, the participants will be randomized to interventional and placebo control arms. Enrollment into interventional and placebo arms will be stratified at one level by the presence or absence of pre-existing self-reported diabetes mellitus utilizing separate randomization tables. The University of Pittsburgh Medical Center Investigational Drug Service (UPMC-IDS) will be responsible for randomization, blinding, and providing the study infusion at the bedside to the clinical team.

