### **5.4.3 Baseline testing and randomization**

- Baseline clinical variable recording
- Pre-intervention capillary blood glucose measurement
- Initial research blood draw (up to 4 hours prior to the start of infusion)
- Aerodigestive tract samples for microbiome analyses (up to 4 hours prior to the start of infusion):
  - Oral swab
  - Tracheal aspirate (if the patient is on mechanical ventilation)
  - Gastric aspirate
- Colonic tract samples for microbiome analyses (up to 4 hours prior to the start of infusion)
  - Rectal swab
  - Stool sample (if available)

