#### 6.3.2 Research blood draws

Blood will be drawn for plasma and serum at two time points (a) at the time of randomization and (b) after the completion of the intervention period. Approximately 10 mL of blood will be drawn each time either by venipuncture or by drawing blood from existing indwelling catheters (central venous lines or arterial lines) by the patient's bedside nurse. Blood will be drawn into several tubes including serum, EDTA, and BD P800 collection tubes.

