### 9.2 Proposed statistical analysis

Primary statistical analysis comparing levels of pro-inflammatory cytokines will be determined by t-test (or non-parametric test if indicated) by intention-to-treat analysis. Differences in secondary continuous outcome variables between intervention and control groups will be determined by t-test or non-parametric test as appropriate. Differences in dichotomous secondary outcomes (development of

hyperglycemia, in-hospital mortality, etc.) will be determined by chi-squared analysis or Fisher's exact test as appropriate.

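### Section 9.1 names chance baseline imbalance as a reason to enrol 36 rather than 7 per arm, but the primary test in section 9.2 uses neither the baseline blood sample nor the diabetes stratum

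*Combined protocol and SAP*

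**What the plan says.** Section 9.1 states that "recruitment of 7 patients in each group will provide 90% power to detect a 15% difference in IL-6 with an alpha error of 0.05". It then gives two reasons for going higher: "we will need to consider the risk of unbalanced baseline characteristics in our sample and allow for dropouts as well". The conclusion is that "36 patients will be enrolled in each group, which will provide greater than 90% power to detect 15% difference in IL-6". It gives no standard deviation, dropout rate, allowance for imbalance or formula for the step from 7 to 36.

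Section 9.2 says the primary comparison of cytokine levels "will be determined by t-test (or non-parametric test if indicated) by intention-to-treat analysis". It names no covariate or stratum term.

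The material for an adjusted analysis is already being collected. Section 6.3.2 says "Blood will be drawn for plasma and serum at two time points (a) at the time of randomization", the second being after the intervention, and section 5.4.3 lists the first sample among the baseline procedures: "Initial research blood draw (up to 4 hours prior to the start of infusion". Section 5.2.3 says allocation is "stratified at one level by the presence or absence of pre-existing self-reported diabetes mellitus".

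**The concern.** The plan identifies a specific threat to a single 72-patient comparison: arms that differ at baseline by chance. It then leaves that threat out of the primary analysis. Sample size and covariate adjustment do different jobs here. More patients make the arms more alike in absolute terms, but they also make the test sensitive to smaller differences, in the same proportion. If the arms happen to start apart on IL-6, an unadjusted comparison at 24 hours carries part of that starting difference into the estimate and the p-value. Depending on its direction, it can mimic an effect or hide one. Deciding to adjust only after an imbalance has been seen would be a data-driven choice, so the analysis needs to be fixed in advance.

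**Working it through.** **Inputs.** From section 9.1: 7 and 36 per arm, a 15% difference, alpha 0.05. From the synopsis: 72 patients, 1:1. Not in the documents, so assumed: two-sided testing, dropout of 10 to 30%, and a baseline-to-24-hour IL-6 correlation (rho) of 0.3, 0.5 or 0.7.

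**1. The plan's own figure.** No SD is stated, so it has to be back-solved. With noncentral-t power, two-sided, all four rows of Table 9.1 (6, 7, 4, 5 per arm) are reproduced by an SD of about 7.45 to 7.90% of the mean (one-sided: 8.70 to 9.00%). For example, at an SD of 7.7%, 7 per arm has 91.6% power. At that SD, 36 per arm has more than 99.99%, so the claim of over 90% follows on the plan's own terms.

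**2. Dropouts.** Enrolment needed for 7 evaluable patients is 7/(1 − L):
- L = 10%: 7.78, so 8
- L = 20%: 8.75, so 9
- L = 30%: 10

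That accounts for 1 to 3 of the 29 extra patients per arm. Dropout alone would have to reach 1 − 7/36 = 80.6%. Section 7.6 also limits loss of samples when tube feeding replaces the infusion: "Research specimens will still be collected for these participants".

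**3. Absolute imbalance.** The SD of a standardised baseline difference is √(2/n): 0.535 at 7 per arm and 0.236 at 36. The ratio is √(7/36) = 0.44, a fall of 56%. The chance of a gap above 0.5 SD drops from 35.0% to 3.4%. In this sense the larger sample does help.

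**4. Imbalance relative to its standard error.** The chance that the baseline difference is at least 1.5 SE is 2[1 − Φ(1.5)] = 13.4%, which does not depend on n. With no treatment effect, the standardised outcome difference is

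Z(24 h) = rho × Z(baseline) + √(1 − rho²) × independent noise.

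A 1.5 SE baseline gap at rho = 0.5 therefore shifts the outcome contrast by 0.5 × 1.5 = 0.75 SE on average, at any n. In SD units the shift is 0.75 × 0.535 = 0.40 at 7 per arm and 0.75 × 0.236 = 0.18 at 36: smaller in absolute terms, the same to the test.

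False-positive rates from 600,000 simulated null trials per setting (bivariate normal values, two-sided test at 5%):

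| rho | Unadjusted, 7 per arm, gap ≥ 1.5 SE | Unadjusted, 36 per arm, gap ≥ 1.5 SE | Unadjusted, 36 per arm, all other trials | Adjusted for baseline, gap ≥ 1.5 SE, either n |
|---|---|---|---|---|
| 0.3 | 7.7% | 7.9% | about 4.5% | 5.0–5.2% |
| 0.5 | 12.2% | 13.2% | about 3.7% | 5.0–5.2% |
| 0.7 | 18.7% | 20.8% | about 2.6% | 5.0–5.2% |

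The fourth column follows from the overall 5%. For rho = 0.5 it is (5.0 − 0.134 × 13.2)/0.866 = 3.7%. Averaged over all trials the unadjusted rate was 4.99 to 5.07% in every setting. For gaps of at least 1.96 SE (5% of trials) the unadjusted rates at 36 per arm are 9.5, 18.1 and 32.2%, against 4.9 to 5.3% adjusted.

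**5. Precision.** Adjustment multiplies the variance of the treatment contrast by about 1 − rho²: 0.91, 0.75 or 0.51. In unadjusted patients, 36 per arm is then worth 36/(1 − rho²), about 40, 48 or 71 per arm. What this does for power depends on the unstated SD. At the SD implied by Table 9.1, power is already above 99.99% and adjustment adds essentially nothing. At an assumed SD of 25% of the mean, power for a 15% difference is 70.9% unadjusted and 74.9, 82.6 or 94.0% adjusted.

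**The case against.** The strongest reply is that an unadjusted test after randomisation is valid. Its error rate is 5% over all randomisations, and the raised rates apply only to a subset chosen for large imbalance, offset by lower rates elsewhere. That stands. A reader might infer that the planned test has an inflated type I error; the calculation does not support this. The point concerns the interpretation of one trial in which the imbalance named in section 9.1 has actually occurred.

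A second reply is that raising n does deal with imbalance in the ordinary sense of how far apart the arms are. That also stands (step 3), so it would be wrong to say that the larger sample gives no protection. What it leaves unchanged is imbalance relative to the precision of the comparison.

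Third, a reader might infer from step 2 that the remaining 26 or more extra patients per arm rest on imbalance alone. The documents do not establish that. Section 9.1 attaches reference 62 to the sentence giving 36. As printed, item 62 is the sepsis definitions paper, while item 61, cited there for cytokine levels, is a paper on sizing pilot trials. The numbering looks shifted by one, so 36 may come from a pilot-sizing rule that the text does not state.

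Fourth, section 9.1 speaks of baseline characteristics generally, and adjusting for IL-6 and diabetes does not cover severity, age or infection source. Stratification already handles diabetes by design. Both are true. Baseline IL-6 is nevertheless the baseline value of the primary outcome itself, and its sample is already drawn.

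**Conclusion.** The concern holds in a limited form. Section 9.1 names a risk that the primary analysis in section 9.2 does not address, although the plan collects what is needed to address it. In the 13% of trials with a baseline IL-6 gap of at least 1.5 SE, the unadjusted false-positive rate at 36 per arm is about 8, 13 or 21%, compared with about 5% after adjustment. These figures rest on approximately normal values on the analysis scale and on assumed correlations of 0.3, 0.5 and 0.7; the documents give no correlation. If it is near zero, little is gained.

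This is a worthwhile, inexpensive improvement to the analysis, not a flaw that invalidates the trial. It does not show that 36 per arm is too small or too large, or that the trial is underpowered. The missing derivation of 36 from 7 is a secondary reporting point.

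**What to change.** Keep 36 per arm. In section 9.2, before unblinding, pre-specify the primary analysis as a linear model of 24-hour IL-6 on arm, baseline IL-6 and diabetes stratum, on one scale fixed in advance (for example log). State a rule for missing baseline values, and keep the unadjusted test as a sensitivity analysis.

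In section 9.1, say that imbalance is handled by this adjustment. As a reporting matter, also give the assumed SD, its scale, sidedness, dropout rate and the basis of 36, and check references 61 and 62.

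Cost: no extra patients or blood draws. Up to 72 baseline IL-6 assays are needed if they are not already planned; the protocol draws the sample but does not say which analytes are measured at baseline. The model uses 2 of the 70 residual degrees of freedom (72 − 2), leaving 68.

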### 9.2 Proposed statistical analysis

Primary statistical analysis comparing levels of pro-inflammatory cytokines will be determined by t-test (or non-parametric test if indicated) by intention-to-treat analysis. Differences in secondary continuous outcome variables between intervention and control groups will be determined by t-test or non-parametric test as appropriate. Differences in dichotomous secondary outcomes (development of

hyperglycemia, in-hospital mortality, etc.) will be determined by chi-squared analysis or Fisher's exact test as appropriate.

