## 1.0 SYNOPSIS

Design	The study is a prospective randomized double-blinded placebo-controlled clinical trial to test the effects of early enteral dextrose as a therapeutic agent in critically ill patients with sepsis. Primary outcomes are differences in circulating plasma levels of the pro-inflammatory cytokine IL-6 to be tested 24 hours after randomization. Secondary outcomes include differences in circulating incretin hormone levels, differences in other pro-inflammatory cytokines including IL-1 $\beta$ and TNF- $\alpha$ , changes in intestinal microbial composition and function after intervention, glycemic control and variability as assessed by capillary blood glucose measurements and exogenous insulin dosing during the intervention period, and clinical outcomes including intensive care unit (ICU) and hospital stay and in-hospital mortality.
Duration	Study participants will be randomized within 48 hours of meeting sepsis criteria, undergo a 24 hour intervention and data collection period, and will be followed for clinical outcomes.
Sample Size	72 participants (36 patients in each arm)
Population	Men and women older than 18 years of age with evidence of sepsis admitted to the intensive care unit with an existing enteral feeding tube (or with imminent plans to place one).
Regimen	Participants will be randomized to either receive early low level enteral infusion of dextrose (intervention) or enteral free water (placebo control).

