## 5.0 RESEARCH DESIGN AND METHODS

This study is a single-center, prospective, double-blinded, randomized placebo-controlled clinical trial to determine the therapeutic effects of early enteral dextrose in critically ill patients admitted with sepsis. This trial will have an interventional arm in which participants receive a low level enteral dextrose infusion and a placebo control arm in which participants will receive an enteral free water infusion. The primary outcome of this study is the extent of systemic inflammation as determined by circulating levels of the pro-inflammatory cytokines IL-6 measured at the end of the intervention. Secondary outcomes include measures of glycemic control by capillary blood glucose; measures of insulin, C-peptide, and the incretin hormones glucose-dependent insulinotropic peptide (GIP) and glucagon-like peptide-1 (GLP-1); measures of other pro-inflammatory cytokines including IL-1 $\beta$  and TNF- $\alpha$ ; determination of the composition and function of the aerodigestive tract and colonic microbiome; and clinical measures (including incidence of emesis, ICU length of stay, hospital length of stay, mortality).

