#### 5.1.1 Inclusion criteria

1. Adults aged 18 years and older admitted to an ICU at UPMC Presbyterian, UPMC Montefiore, UPMC Shadyside, or UPMC McKeesport.
2. New presentation of sepsis characterized by a confirmed or suspected infection, with an acute increase from baseline in a modified Sepsis-Related Organ Failure Assessment (SOFA) score of greater than or equal to 2 points (Appendix 11.1). If baseline values are unknown, baseline SOFA score of 0 will be assumed.
3. Available enteral access defined by: (1) an existing nasogastric or orogastric tube, (2) plans to place a nasogastric or orogastric tube, or (3) an existing percutaneous endoscopic gastrostomy (PEG) tube.
4. Less than 48 hours since meeting criteria for sepsis.
5. Expected to stay at least 24 hours in the ICU.

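### The primary IL-6 test is valid but unadjusted: it uses neither the pre-infusion sample nor the diabetes stratum, so it gives up precision and leaves chance imbalance uncorrected

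*Combined protocol and SAP*

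**What the plan says.** The primary analysis is the sentence in Section 9.2: "Primary statistical analysis comparing levels of pro-inflammatory cytokines will be determined by t-test (or non-parametric test if indicated) by intention-to-treat analysis". The rest of that section covers secondary outcomes with tests of the same kind. No section mentions a covariate, a change from baseline or a stratified test.

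The data for an adjusted analysis are nearly all in hand:

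- Section 5.4.3 lists "Initial research blood draw (up to 4 hours prior to the start of infusion"), and Section 6.3.2 confirms "Blood will be drawn for plasma and serum at two time points (a) at the time of randomization" and again after the intervention.
- Section 5.2.3 states "Enrollment into interventional and placebo arms will be stratified at one level by the presence or absence of pre-existing self-reported diabetes mellitus", with a separate randomisation table for each stratum.

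The endpoint is defined only after treatment. The Synopsis says "Primary outcomes are differences in circulating plasma levels of the pro-inflammatory cytokine IL-6 to be tested 24 hours after randomization"; Section 5.0 refers to "circulating levels of the pro-inflammatory cytokines IL-6 measured at the end of the intervention". Nowhere is it stated that IL-6 will be assayed in the baseline plasma.

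Section 9.1 recognises the imbalance problem ("we will need to consider the risk of unbalanced baseline characteristics in our sample") and answers it, together with dropout, by raising enrolment from 7 to 36 per arm.

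**The concern.** Entry is allowed at any point within the window "Less than 48 hours since meeting criteria for sepsis" (Section 5.1.1), so patients may start the infusion with very different IL-6 levels. If a patient's baseline value predicts the 24 h value, leaving it out puts explainable variation into the error term and widens the confidence interval.

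A larger sample makes a chance difference in baseline IL-6 smaller on average, but it does not correct the difference that actually occurs. Stratification balances diabetes by design and does nothing directly for IL-6. A trial with a sizeable baseline difference would therefore report a treatment estimate partly made up of that difference, with no prespecified way to remove it. An adjustment added after unblinding would look post hoc.

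**Working it through.** **Inputs from the documents.** 36 per arm (Synopsis, Section 9.1); alpha 0.05, sidedness not stated, taken here as two-sided; target difference 15%; mouse effect about 40% (Section 9.1).

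**Assumptions.** The documents give neither the SD of IL-6 nor r. I use SD(ln IL-6) of 1.0 and 1.5, r from 0.2 to 0.7, equal variances and 36 evaluable patients per arm.

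**1. The plan's own figure.** Table 9.1 (6, 7, 4 and 5 per group) cannot be derived forwards without an SD. Solving backwards, a two-sided t-test reproduces all four rows if the SD is about 7.5–7.9% of the mean (8.7–9.0% if one-sided). With either SD, power at 36 per arm exceeds 99.9% for a 15% difference, so the claim of more than 90% follows, and adjustment would add nothing visible.

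**2. Variance reduction.** Adjusting for baseline multiplies the variance by 1 − r², so 36 adjusted is worth 36/(1 − r²) unadjusted:

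| r | 1 − r² | Equivalent n per arm |
|---|---|---|
| 0.2 | 0.96 | 37.5 |
| 0.3 | 0.91 | 39.6 |
| 0.5 | 0.75 | 48.0 |
| 0.7 | 0.51 | 70.6 |

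**3. Power.** SE = SD × √(1 − r²) × √(2/36), with √(2/36) = 0.2357. The noncentrality is |ln(1 − reduction)|/SE, on 70 df unadjusted and 68 df adjusted. Worked case, 40% reduction and SD 1.0: |ln 0.6| = 0.511. Unadjusted, 0.511/0.2357 = 2.17, power 57%. At r = 0.5, SE = 0.2041, 0.511/0.2041 = 2.50, power 69%.

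| True reduction, SD(ln) | Unadjusted | r = 0.2 | r = 0.3 | r = 0.5 | r = 0.7 |
|---|---|---|---|---|---|
| 15%, 1.0 | 10.4% | 10.7% | 11.0% | 12.3% | 15.9% |
| 15%, 1.5 | 7.4% | 7.5% | 7.6% | 8.2% | 9.7% |
| 40%, 1.0 | 57% | 59% | 61% | 69% | 85% |
| 40%, 1.5 | 30% | 31% | 32% | 38% | 51% |

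Simulation (10,000 trials per setting) agreed to about a point. The rank test came slightly below the log t-test: 54–55% for a 40% reduction at SD 1.0. At r = 0 the calculated loss from adjusting is below 0.1 point.

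**4. Precision at SD 1.0.** The smallest reduction detectable with 80% power is 49% unadjusted, against 47%, 44% and 38% at r = 0.3, 0.5 and 0.7. The 95% CI for the ratio of geometric means is the estimate multiplied and divided by 1.60 unadjusted, against 1.57, 1.50 and 1.40.

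**5. Validity.** Simulated rejection under the null, SD 1.0–1.5: rank test 4.5–5.3%, log t-test 4.8–5.2%, adjusted model 4.8–5.4%.

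**6. Chance imbalance.** The baseline mean difference has an SE of 0.236 SD. One SE shifts the unadjusted ratio by exp(r × 0.236) = 1.07, 1.13 and 1.18 at r = 0.3, 0.5 and 0.7 (SD 1.0). Given an imbalance of k SE, the unadjusted statistic under the null is roughly normal with mean kr and SD √(1 − r²). For k = 1, the two-sided rejection rate is 5.0%, 4.8% and 3.9%. For k = 2, it is 8.1%, 13.4% and 21.6%. Simulating the rank test at k = 2 gave 7.9%, 12.4% and 20.3%, against 4.9–5.2% for the adjusted model. An imbalance of two SE or more, in either direction, arises in about 5% of trials.

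**7. Diabetes stratum.** The documents give no diabetes effect on IL-6, so its contribution cannot be sized. As an illustration only, suppose 35% of patients are diabetic and diabetes shifts the outcome by 0.5 SD. With balanced strata, the unadjusted t-test becomes slightly conservative (type I error 4.0–4.7%), and its power for a 0.6 SD treatment effect falls from about 72% to 68–69%.

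**The case against.** An unadjusted intention-to-treat comparison of a randomised outcome is a legitimate choice, and nothing here invalidates it. Every gain rests on an r that the documents do not give. Variable entry times could weaken the baseline-to-24 h correlation as easily as they widen the baseline spread. The large power gains are for a 40% reduction, the mouse effect, which Section 9.1 itself calls much larger than the effect the trial is powered for. At 15%, adjustment hardly changes the outcome. Inflated conditional error is confined to the tail, and diabetes is already balanced by stratification.

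Most of this is true, and it sets the size of the point without removing it. The issue is efficiency and conditional protection, not an error. But not knowing r does not argue against adjusting: the calculated loss at r = 0 is negligible and the gain grows with r. A 15% effect cannot be found by either analysis at the assumed SDs, and is found by both at the SD implied by Table 9.1. Adjustment matters between those extremes, where a trial of this size could plausibly detect an effect. The diabetes term is the lesser part of the point.

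**Conclusion.** The concern holds, as something that should be changed rather than something that must be. Section 9.2 leaves out a baseline measurement that the trial could have from blood it already draws, and a factor used in its randomisation. The test keeps its overall validity. At r of 0.3 to 0.7 the loss is equivalent to about 4 to 35 patients per arm (36 against 40 to 71); at r of 0.2 it is under 2. The imbalance that Section 9.1 worries about is made less likely but is not corrected if it occurs. The textual gap is certain. The size of the benefit depends on the assumed SD and r.

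**What to change.** Before unblinding, make the primary analysis a linear model of log 24 h IL-6 on treatment, log baseline IL-6 and diabetes stratum, with participants analysed in the arm to which they were randomised. Report the ratio of geometric means with its 95% CI, and state in Section 9.1 that the percentage difference is meant on that scale. Keep the unadjusted rank test as a sensitivity analysis.

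The plan should also:

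- state that IL-6 will be assayed in the baseline plasma;
- say how a missing baseline value is handled so that nobody is dropped for it, for example by imputing the pooled baseline mean;
- use the same model for the other analytes if they are assayed at both draws.

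Missing 24 h values need their own rule; this change does not supply one.

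The cost is SAP wording and two degrees of freedom (70 to 68). If the baseline assay is not already planned, add one IL-6 assay per participant, at most 72, on plasma already drawn. No extra patients or blood draws are needed.
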